mITD	Modified Intention-to-diagnose
PP	Per Protocol population
EFS	Evalued for Safety Set
DSMB	Data and safety monitoring board
EAC	Endpoint adjudication committee
ACS	Acute coronary syndrome
hs-cTn	High-sensitivity cardiac Troponin
mRS	Modified Rankin Scale NIHSS
MoCA	Montreal Cognitive Assessment
PSS	Perceived Stress Scale
IADL	Lawton Instrumental Activities of Daily Life Scale
NIHSS	National Institutes of Health Stroke Scale
TICS	Telephone Interview with Cognitive Status
mRS	Modified Rankin Scale NIHSS
TIA	Transient ischemic attack
MI	Myocardial infarction
ROC	Receiver-Operating-Characteristic
AUC	Area under the curve

1 Introduction

This Statistical Analysis Plan (SAP) is based on the study protocol version 1.1 of June 19, 2018 (also published in (Nolte, et al. 2020)) and follows the guideline for statistical analysis plans (Gamble, et al. 2017)

Some points of the statistical methods and of the study design are already described in the study protocol. This Statistical Analysis Plan (SAP) aims to further specify the procedures and statistical methods applied during the final analysis of the study data.

1.1 Background and rationale

Elevation of cardiac troponin can be found in about 30% of patients with acute ischemic stroke (depending on the assay and cut-off used). Elevated troponin indicates increased mortality in stroke patients. There is currently little evidence regarding the ideal care of these patients. The investigators know from previous studies that approximately 25% of acute stroke patients with elevated levels of cardiac troponin have culprit lesions on coronary angiogram.

The primary goal of the PRAISE study is to develop a diagnostic algorithm that allows the prediction of an acute coronary syndrome (ACS) in stroke patients. To achieve this, clinical symptoms, troponin levels as well as findings on ECG, echocardiography and coronary angiography will be systematically evaluated. The PRAISE study is a multicenter study with more than 25 sites in Germany. Acute ischemic stroke patients with elevated troponin level are eligible for participation in the study. The primary endpoint is the diagnosis of acute coronary syndrome as established by an independent endpoint committee.

1.2 Objectives

The primary goal of the multicenter PRAISE study is to develop a diagnostic algorithm to better identify ACS as origin of troponin elevation in patients with an acute ischemic stroke. The primary hypothesis will test whether dynamic troponin levels (as compared to stable ones) indicate presence of ACS. The following hypotheses will be tested:

Primary hypothesis: A dynamic troponin elevation (>50% change at measurement after 3 hours) indicates an ACS in patients with an acute ischemic stroke. The change in troponin level (dynamic vs. stable after 3 hours) within patients with an acute ischemic stroke can be used to differentiate whether an ACS is present.

Endpoint: diagnosis of “ACS”, determined by an independent endpoint adjudication committee.

1. Secondary hypothesis: Stroke patients with dynamic troponin change have a worse functional outcome three or twelve months after the event in comparison to those with stable troponin.

Endpoints: Modified Rankin-Scale (mRS) after three and twelve months.

2. Secondary hypothesis: Stroke patients with dynamic troponin change have an increased risk for recurrence of cardiovascular events and a higher mortality rate in comparison to those with stable troponin.

Endpoints: Brain infarcts, transient ischemic attack (TIA), myocardial infarction (MI) and death as well as the combined endpoint thereof (MACE) during the acute inpatient stay, after three and twelve months.

In addition, in an exploratory approach we want to establish a combined rule-in/rule-out diagnostic algorithm to identify the subgroup of troponin-positive stroke patients in whom the diagnosis of ACS (i.e. type I vs. type II MI) vs. not is made by means of coronary angiography including stroke-specific cut-off values for troponin and other biomarkers, the value of ECG, echocardiography, clinical parameters, and combinations thereof.

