Functional outcome will be measured using the modified Rankin Scale (mRS)¹⁶ as well as the Lawton Instrumental Activities of Daily Life Scale (IADL)¹⁷ three and twelve months after the index event.

Second secondary hypothesis:

Ischemic stroke patients with a dynamic change of troponin values have poorer cognitive outcome than patients with stable troponin values three and twelve months after the index event.

Endpoint:

Cognitive outcome will be evaluated using the Montreal Cognitive Assessment (MoCA)¹⁸ and the Telephone Interview for Cognitive Status (TICS)¹⁹

Third secondary hypothesis:

Ischemic stroke patients with a dynamic change of troponin values have an increased risk of recurrent cardiovascular events and mortality compared to patients with stable troponin values.

Endpoint:

Rates of recurrent ischemic strokes, TIA, myocardial infarction and mortality after three and twelve months.

Study population:

According to the sample size calculation, 251 stroke patients will be included prospectively. Both male and female patients will be included. Pregnant or breastfeeding patients will not be eligible for inclusion. The study will only recruit patients ≥ 18 years of age.

Inclusion criteria:

- age ≥ 18 years
- written informed consent
- diagnosis of ischemic stroke based on clinical symptoms and imaging (cranial CT or MRI) < 72 h after symptom onset
- troponin elevation:
 - a) either highly abnormal initial troponin levels (Elecsys-Assay hs-cTnT > 52 ng/l, Architect-Assay hs-cTnI > 52 ng/l²⁰, Dimension Vista Assay hs-cTnI > 107 ng/l²¹)
or
 - b) dynamic troponin elevation with Δ change $> 20\%$ of the initial value after 3 hours and at least one value above the assay-specific upper reference limit according to ESC guidelines¹²
- diagnosis of transient ischemic attack, if the initial focal neurological deficit was objectified by a neurologist during clinical examination and the patient has an ABCD2-Score²² ≥ 4 points
- patient willing to participate in follow-up via telephone interview

Exclusion criteria:

- renal insufficiency (i.e. estimated glomerular filtration rate (eGFR) < 30 ml/min/1,73 m²)²²
- manifest hyperthyroidism
- cerebral infarct > 100 ml on diffusion weighted imaging (DWI-MRI) or on cranial CT (if performed > 24 hours after symptom onset) or ASPECTS-Score²³ < 7 (if cranial CT was performed within 24 hours of symptom onset)
- pregnancy or breast feeding

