2.3 Sample size

To be assessed for eligibility (n = 8,750 patients with ischemic stroke, thereof n = 1,250 with troponin elevation according to the inclusion criteria)

To be allocated to trial (n = 251)

To be analyzed (n = 203)

Full details of sample size calculation can be found in the study protocol.

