5.3 Additional analyses

The primary outcome analysis is repeated in the PP population. Additional analyses of the presence/absence of ACS in relation to presence/absence of dynamic troponin elevation include the calculation of further diagnostic accuracy measures like sensitivity and specificity together with the 95%-confidence interval.

A mediation analysis will be conducted to identify direct and indirect effects of the diagnostic group (dynamic vs. stable) and additionally peak troponin T in patients with available troponin T values (exposure variables) and the presence of ACS (yes vs. no) as well as presence of MI type 1 (yes vs. no) and in patients with ACS MI (Type 1 vs. Type 2) (mediator variables) on mortality and MACE (target outcome) using accelerated failure time models. This will be performed after unblinding of the diagnostic groups and analysed in an explorative manner.

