5.3.3 Prediction

We will calculate the area under the Receiver-Operating-Characteristic-Curves (ROC-analysis) to evaluate the predictive accuracy of changes in troponin alone, and adjusted for the variables found in the step above, particularly relative changes in the 20% to 50% interval, for the presence of ACS, the presence of type 1 myocardial infarction as well as in those patients in whom ACS is present, for the prediction of type 1 vs. type 2 myocardial infarction in stroke patients using Harrell's c statistic to determine the best cut-off to predict ACS as well as type 1 myocardial infarction.

We will calculate a prediction algorithm that identifies patients with ACS with highest area-under-the-curve (AUC) in a ROC-Curve (ROC-analysis of c-statistics) and which takes the results of pre-defined diagnostic procedures into account.

A gender-specific analysis will be conducted to determine if there are different cut-off values by testing an interaction between gender and troponin change.

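### Entry depends partly on the index test, so specificity, negative predictive value, the ROC curve and the cut-off describe only patients who meet the PRAISE troponin rule, not all stroke patients with elevated troponin

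*SAP*

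**What the plan says.** The Protocol's inclusion criteria give two troponin routes.

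- Route (a): "either highly abnormal initial troponin levels (Elecsys-Assay hs-cTnT > 52 ng/l, Architect-Assay hs-cTnI > 52 ng/l", with a separate threshold of 107 ng/l for a third assay. The size of the 3-hour change does not matter.
- Route (b): a change of more than 20% "of the initial value after 3 hours and at least one value above the assay-specific upper reference limit".

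The index test in SAP 1.2 and 5.1.1 is the same 0 to 3 hour change, cut at more than 50%. The primary analysis is a diagnostic odds ratio. SAP 5.3 adds "calculation of further diagnostic accuracy measures like sensitivity and specificity together with the 95%-confidence interval". SAP 5.3.3 plans ROC curves and a best cut-off, "particularly relative changes in the 20% to 50% interval, for the presence of ACS". Both routes are pooled throughout, and neither document plans an analysis by route.

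On the population, SAP 1.1 describes eligibility simply as having an elevated troponin level and states: "Elevation of cardiac troponin can be found in about 30% of patients with acute ischemic stroke". SAP 2.3 expects 8,750 stroke patients to be assessed, "thereof n = 1,250 with troponin elevation according to the inclusion criteria". The algorithm in SAP 1.2 is meant to rule ACS in and out, and so to "identify the subgroup of troponin-positive stroke patients in whom the diagnosis of ACS" is made. SAP 4.2 says the number of ineligible patients will not be reported.

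**The concern.** A patient with a value above the reference limit, a first value not above the high threshold, and a change of 20% or less cannot enter by either route. Every such patient is negative on the index test, and at any other cut-off of 20% or more. Below a 20% change the cohort holds route (a) patients only; above 20% it holds both routes.

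Leaving out test-negative patients changes the denominators of specificity and negative predictive value, and that of sensitivity if any of them has ACS. The pooled figures also depend on the mix of routes recruited. SAP 1.1 and 1.2 can be read as promising results for all stroke patients with elevated troponin. Under that reading, a rule-out statement for stable, moderately raised troponin would rest on no enrolled patients, and the SAP's planned reporting would not show the gap.

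**Working it through.** **Plan figures reproduced.** The pilot counts in the Protocol's sample size section are 11 of 29 dynamic, with a culprit lesion in 6 of 11 dynamic and 1 of 18 stable patients. The odds ratio is (6 × 17)/(5 × 1) = 20.4, as stated. With 6% in stable patients and odds ratio 4, the dynamic risk is 0.2553/1.2553 = 20.3%. With 38% dynamic, 80% power, two-sided 5% and a continuity correction, this gives N = 203, as stated. The point here does not depend on N.

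**Size of the excluded group.** Elevated: 0.30 × 8,750 = 2,625. Outside the rule: 2,625 − 1,250 = 1,375, or 52%. SAP 1.1 says the 30% depends on assay and cut-off, so I varied it:
- at 20%: (1,750 − 1,250)/1,750 = 29%
- at 40%: (3,500 − 1,250)/3,500 = 64%

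**Enrolled accuracy, for illustration.** Pilot rates scaled to 1,250 give 258.6 true positives, 215.5 false positives, 43.1 false negatives and 732.8 true negatives. Sensitivity is 6/7 = 86%, specificity 17/22 = 77%, positive predictive value 6/11 = 55% and negative predictive value 17/18 = 94%.

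**Adding the excluded.** Let r be their ACS risk, which neither document gives. All are test-negative, so:
- sensitivity = 258.6/(301.7 + 1,375r)
- specificity = (732.8 + 1,375(1 − r))/(948.3 + 1,375(1 − r))

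| Assumed r | Sensitivity | Specificity | Negative predictive value | Odds ratio |
|---|---|---|---|---|
| enrolled only | 86% | 77% | 94% | 20 |
| 0% | 86% | 91% | 98% | 59 |
| 2% | 79% | 91% | 97% | 35 |
| 1/18 | 68% | 90% | 94% | 20 |
| 10% | 59% | 90% | 92% | 13 |

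Positive predictive value stays at 55% in every row, because every patient with a change above 50% and one value over the reference limit meets the troponin rule.

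**Cut-off.** For any threshold of 20% or more, adding the excluded multiplies sensitivity by 301.7/(301.7 + 1,375r) and the false-positive rate by 948.3/(948.3 + 1,375(1 − r)). At r = 1/18 these are 0.80 and 0.42. For a dichotomised marker the c statistic is (sensitivity + specificity)/2. Because the two factors differ, the threshold that maximises it can move. Below 20% no threshold can be assessed in patients whose first value is not above the high threshold.

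**Mix of routes within the cohort.** Hold the ACS risks at 6/11 and 1/18 and let route (b) rise from 0% to 50% of patients. The dynamic share becomes 0.5 × 11/29 + 0.5x, where x is the dynamic share in route (b). This is an assumption, since the documents give no value.
- x = 70%: sensitivity 92%, specificity 64%
- x = 50%: 88.5%, 73%
- x = 38%: unchanged
- x = 30%: 83%, 80%

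**The case against.** The strongest reply is that troponin-positive may simply mean meeting the entry rule. SAP 2.3 ties elevation to the inclusion criteria, and so does the Protocol's troponin section. On that reading the estimates do apply to the population named. This stands as a possible reading, but the SAP does not state it and SAP 1.1 uses elevation in the wider sense.

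It is also fair that the algorithm is labelled exploratory and the accuracy measures additional, although SAP 1.2 names a diagnostic algorithm as the primary goal. SAP 5.3.2 adjusts the odds ratio for peak troponin T, which partly covers differences in level. It does nothing for sensitivity, specificity or the cut-off.

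A reader might infer more than the documents support:
- **That sensitivity must be inflated.** It falls only if some excluded patients have ACS; at zero risk it stays at 86%.
- **That the 20% to 50% search crosses a break in eligibility.** The break lies at the lower edge of that interval, not inside it. What remains is the part of the curve below 20% and a possible shift of the optimum.
- **That more route (b) patients must raise sensitivity and lower specificity.** The direction reverses if route (b) has a smaller dynamic share than the pilot. The Protocol expects a higher dynamic share in PRAISE than in the pilot, which supports the direction but not a size.
- **That the SAP already makes a rule-out claim for stable, moderately raised troponin.** It makes none; the risk lies in how the results may later be read.

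**Conclusion.** The point holds as one about scope. The entry rule selects partly on the index test. Pooled specificity, negative predictive value, the full ROC curve and the chosen cut-off therefore describe the entry-rule population and its mix of routes, as does sensitivity if any excluded patient has ACS. They do not carry over to all stroke patients with elevated troponin.

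A reader might conclude that the primary analysis fails. The documents do not support that: the odds ratio still tests association among enrolled patients, though its value carries over to the wider group only if the excluded have the same ACS risk as enrolled stable patients.

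The 52% combines a rounded background prevalence with a screening projection. The accuracy figures use 29 pilot patients, all with first values above 50 ng/l and with culprit lesions rather than adjudicated ACS, and they apply those rates to both routes. They illustrate size and are not forecasts. Specificity shifts upward at every assumed risk shown. This should be corrected in the SAP, but nothing in the primary test needs to change.

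**What to change.** In SAP 1.2, state that accuracy measures and cut-offs apply to patients who meet the PRAISE troponin entry rule, and that no rule-out claim will be made for stable, moderately raised troponin.

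In SAP 5.3 and 5.3.3, keep the pooled estimates and add sensitivity, specificity, ROC curve and cut-off by entry route. The routes overlap, so fix the assignment in advance: route (a) is any patient whose initial local-assay value exceeds that assay's high threshold, and route (b) is everyone else. Use the local values that determined eligibility, not the core-laboratory re-measurements. Route (a) enrolled the full range of change. Report route (b) only for thresholds of 20% or more.

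A route-stratified odds ratio is optional and supportive only. If half of 203 patients came by route (b) and 70% of those were dynamic (both assumptions), the stable route (b) cell would hold 203 × 0.5 × 0.3 ≈ 30 patients and, at 1/18, about 1.7 ACS cases.

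The cost is SAP wording and a few tables from data already held, wider route-specific intervals, and a narrower claimed population. Eligibility, data collection and the primary test stay as they are.

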1.2.1 Primary Outcome

The primary outcome is defined as presence of ACS within seven days of admission to hospital (“V2”) defined by an independent endpoint adjudication committee on individual patient basis (i.e. ST-elevation myocardial infarction STEMI, Non-STEMI, and unstable angina vs. other cardiac and non-cardiac).

1.2.2 Main Secondary Outcomes

The secondary outcome parameters are defined as:

- Mortality (recorded at 1 week, 3- and 12-months follow-up)
- Cardiovascular events (new stroke, TIA, MI; at 1 week, 3- and 12-months follow-up)
- Combined vascular endpoint (MACE, i.e. mortality plus cardiovascular endpoints as above)
- Functional outcome (mRS; at baseline, 1 week, 3- and 12-months follow-up)
- Imaging (Stroke location and size, degree of cerebral white matter damage)
- New hospital admission

During the course of the study it turned out that the imaging procedure and count of hospital admission were not realisable. Therefore, these endpoints cannot be analysed.

1.2.3 Safety Outcome Parameters

Documentation of SAEs and assessment by a critical event committee (CEC), regular review by a data and safety monitoring board (DSMB).

Procedure-related complications of coronary angiography: clinically manifest stroke, renal failure, hematoma at site of puncture (groin); assessment by independent data and safety monitoring board. For definition of serious adverse events of special interest see study protocol.

2 Study Methods

2.1 Trial design

Observational, prospective, phase III ((Pepe 2003), (Zhou, Obuchowski und McClish 2011)), multicenter diagnostic trial with blinded endpoint assessment of pre-defined endpoints.

All patients receive troponin measurement at hospital admission (defined as 0 hrs) and again at 3 hrs. For details of target condition, index text and reference standard see study protocol.

2.2 Randomization

For this type of study, a randomization was not required (within-subject design). Troponin progression measurement and coronary angiography are performed in all patients.

2.3 Sample size

To be assessed for eligibility (n = 8,750 patients with ischemic stroke, thereof n = 1,250 with troponin elevation according to the inclusion criteria)

To be allocated to trial (n = 251)

To be analyzed (n = 203)

Full details of sample size calculation can be found in the study protocol.

2.4 Framework

Prospective, single-arm, multicenter, phase 3 diagnostic accuracy study.

2.5 Interim analyses

Interim analyses in terms of efficacy will not be performed.

2.6 Timing of final analysis

All outcomes will be analysed collectively after the last follow-up and data cleaning process are finished.

The final analysis of the primary endpoint will take place after the database has been reviewed for completeness and accuracy and is determined by the Endpoint Adjudication Committee to be complete.

The results will be reported according to the STARD Statements ((Bossuyt, et al. 2003))

2.7 Timing of outcome assessments

A detailed schedule of the planned outcome collection is given in table 1 of the study protocol (Nolte, et al. 2020).

The primary outcome, presence of ACS, is assessed within 7 days of hospital admission (“V2”). Follow-up measurements will be carried out after 3 (“V3”) and 12 months (“V4”).

3 Statistical Principles

3.1 Confidence intervals and *P* values

All applicable statistical tests will be two-sided and will be performed using a 5% significance level. Analyses of secondary outcomes will be performed without adjustment for multiplicity. All confidence intervals presented will be 95% and two-sided.

3.2 Adherence and protocol deviations

Adherence is not relevant in this study, since there is no therapeutic intervention for study purposes to be followed.

All protocol violations will be documented and classified as major or minor in a blinded manner by an independent staff member who is not involved in the study process.

A major protocol deviation occurs if contrary to the study protocol a patient could not receive a coronary angiography. The following reasons are listed:

- Data from coronary angiography are not provided for technical reasons.
- Patient refuses coronary angiography.
- Clinician declines coronary angiography for medical reasons.
- Coronary angiography is not performed for capacity reasons.
- A transfer of images from the ultrasound scanner is not possible for technical reasons.

Further, a major protocol deviation occurs if a troponin measurement is not available.

These patients will not be taken into regard into the primary analysis.

A minor protocol deviation occurs if a patient could not receive echocardiography. The following reasons are listed:

- Based on clinical indication, a transesophageal echocardiography is performed, which is not relevant for the objective of this trial.
- Echocardiography is not performed for capacity reasons.

Patients with minor protocol deviations are included in the primary analysis.

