3.3 Analysis populations

3.3.1 Modified Intention to diagnose Population (mITD)

The primary analysis population is the mITD (intention to diagnose) population. The mITD population consists of all patients in whom troponin measurements at 0 and 3 hours were available.

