3.3.2 Per Protocol population (PP)

The Per Protocol population includes all patients who have no major protocol violation. In particular coronary angiography must have been performed.

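### SAP 3.2 classes a failed echocardiography image transfer as a major deviation, although a missing echocardiogram is only minor; this can remove evaluable patients from the per-protocol set and conflicts with the mITD definition

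*SAP*

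**What the plan says.** SAP 3.2 opens its list of major deviations with this condition: "A major protocol deviation occurs if contrary to the study protocol a patient could not receive a coronary angiography". Five reasons follow. Four concern angiography: data not provided for technical reasons, refusal by the patient, a medical decision against it, and lack of capacity. The fifth is "A transfer of images from the ultrasound scanner is not possible for technical reasons". A missing troponin measurement is then added as a further major deviation, followed by the sentence "These patients will not be taken into regard into the primary analysis".

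The next paragraph deals with echocardiography: "A minor protocol deviation occurs if a patient could not receive echocardiography". Its two listed reasons are a transesophageal examination done instead on clinical grounds, and "Echocardiography is not performed for capacity reasons". For this group the SAP says "Patients with minor protocol deviations are included in the primary analysis".

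The populations are defined separately. SAP 3.3.1: "The mITD population consists of all patients in whom troponin measurements at 0 and 3 hours were available". SAP 3.3.2: "The Per Protocol population includes all patients who have no major protocol violation"; it adds that angiography in particular must have been done. SAP 5.1.1 runs the primary analysis in the mITD population, and SAP 5.3 repeats it in PP.

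**The concern.** The fifth reason does not belong under its heading. A failed transfer from an ultrasound scanner does not show that angiography was missed, and technical failure of angiography data already has its own entry. The classification is also inverted, because a patient whose echocardiogram was done but could not be uploaded is treated more severely than a patient who had none.

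At stake is who counts in PP and, depending on which section is followed, in the primary analysis. The primary comparison needs the troponin change from 0 to 3 hours and the adjudicated diagnosis of acute coronary syndrome; PP additionally requires angiography. Patients who have all of these could be removed because of an upload problem. The classification is made by a staff member outside the study process, who has only the written list to go by, so the wording decides the outcome.

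**Working it through.** **Step 1. What the ultrasound images are.** The only ultrasound examination in either document is echocardiography. Protocol, Echocardiography, has transthoracic images uploaded for central reading. Angiography images are uploaded too (Protocol, Coronary angiography), but they do not come from an ultrasound scanner, and the first entry in the SAP 3.2 list already covers missing angiography data.

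**Step 2. Apply the rules to two patients.** Both have troponin at 0 and 3 hours and an angiogram.

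| | Patient A: echo done, images not transferable | Patient B: no echo, lack of capacity |
|---|---|---|
| Class under the SAP 3.2 lists | major | minor |
| PP (SAP 3.3.2) | out | in |
| Primary analysis, exclusion sentence in SAP 3.2 | out | in |
| Primary analysis, mITD in SAP 3.3.1 | in | in |
| Core-laboratory wall-motion variable (SAP 5.3.2) | missing | missing |

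The two patients lack the same core-laboratory variable but are classed differently. For patient A, the third and fourth rows contradict each other.

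**Step 3. The plan's own sample size.** Inputs from Protocol, Sample size calculation: odds ratio 4, risk with stable troponin p0 = 0.06, dynamic share 11/29, power 80%, alpha 0.05. The test is two-sided by SAP 3.1.

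- Odds with dynamic troponin = 4 × 0.06/0.94 = 0.2553, so p1 = 0.2553/1.2553 = 0.2034.
- Ratio of stable to dynamic patients r = 18/11; pooled risk p = (p1 + r·p0)/(1 + r) = 0.1144.
- n1 = [1.960·√((1+r)·p(1−p)) + 0.842·√(r·p1(1−p1) + p0(1−p0))]² / [r(p1−p0)²] = 66.0.
- Continuity correction: (n1/4)·[1 + √(1 + 2(1+r)/(n1·r·(p1−p0)))]² = 76.8, rounded up to 77.
- Total = 77 × 29/11 = 203, which is the planned figure.

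Reclassifying the ultrasound item does not change this number.

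**Step 4. Size of a loss.** Neither document gives a transfer-failure rate. I assume 5% to 10% of 203.

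- Patients lost: 0.05 × 203 = 10; 0.10 × 203 = 20.
- Cases lost at the 24% (7/29) culprit-lesion rate that the protocol takes from the earlier TRELAS study: 0.24 × 10 = 2.4; 0.24 × 20 = 4.8. The rate of acute coronary syndrome in PRAISE may differ.
- Width of the confidence interval for the log odds ratio, if the loss is proportional across cells: 1/√0.95 = 1.026; 1/√0.90 = 1.054. That is about 3% to 5% wider.
- Power without continuity correction, odds ratio 4, same r, solving the Step 3 formula for power, with the stable-group risk taken as 1/18 (the unrounded value behind the 6%): 83.2% at 203 patients, 81.5% at 193 and 79.5% at 183.

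**The case against.** Four points can be made for the plan.

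First, the heading of the list requires that angiography was not received. Patient A had an angiogram, so on a strict reading the heading is not met and the item excludes nobody. That is a possible reading. However, the first entry (angiography data not provided) also goes beyond the heading, so the list does not hold to it. If the heading does control, the fifth item has no function and is still misplaced.

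Second, mITD depends on the two troponin values alone, and the primary analysis is run in mITD. This stands. A reader might infer that these patients are definitely lost from the primary analysis, but the documents do not support that. The exclusion sentence in 3.2 directly follows the one on missing troponin and could be meant only for those patients. The contrasting sentence on minor deviations suggests that it covers all major ones. The text leaves this open.

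Third, echocardiography is not irrelevant to the endpoint. The protocol has the adjudication committee consider it together with angiography, ECG and symptoms. This also stands, but it cannot explain the rule, because having no echocardiogram would then be at least as serious and the SAP calls it minor.

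Fourth, the assumed loss is applied to 203, which is already net of the allowance from 251, so some of it might be absorbed there. The protocol gives withdrawal of consent as the only reason for that allowance.

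**Conclusion.** The rule is wrong as written, with minor impact. The ultrasound item is out of place in the major list, and its effect is the reverse of how the SAP treats a missing echocardiogram. The exclusion from PP follows if the list is applied item by item. For the primary analysis the finding is a conflict between 3.2 and 3.3.1, not an established exclusion.

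The numerical effect is probably small: an interval about 3% to 5% wider and a loss of about 2 to 4 percentage points of power (83.2% to 81.5% or 79.5%). Both rest on the assumed 5% to 10% failure rate.

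Two further inferences go beyond the documents. A reader might suppose that failures cluster by centre and so bias the result. That is possible, since equipment is local, but neither document reports such a pattern. Differing local assays are handled by central re-measurement (Protocol, Methods against bias), and deviations are classified blinded. A reader might also say that a patient without an echocardiogram is kept in every analysis. That patient stays in the primary and PP analyses, but lacks the wall-motion regressor of SAP 5.3.2 and, without imputation, drops out of any model that uses it.

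**What to change.** Before unblinding:

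1. Move the ultrasound-transfer item in SAP 3.2 from the major to the minor (echocardiography) list, worded as echocardiography performed but core-laboratory reading unavailable. If the current placement is deliberate, state the reason and explain why a missing echocardiogram is treated more leniently.
2. Reword the exclusion sentence in 3.2 so that it names the deviations and the population it applies to and agrees with 3.3.1 and 3.3.2.
3. Re-class any deviations already recorded under this item, and report how many there were, by centre.

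These patients then stay in PP and in the primary analysis, and only the core-laboratory echocardiography variable is missing in models that use it. The cost is a short SAP amendment and a check of the deviation log. No new data are needed and the sample size does not change.
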